RESULTS: Age was equally distributed between treatment & placebo groups. 57% of the arginine treatment group & 46% of the placebo group were female. The overall time between triage in the emergency department or presentation to clinic and delivery of first randomized study drug dose was 20.4 ± 11 hours, with no difference between the placebo and treatment arm. A significant reduction in narcotic use (defined as total opioid use over the course of the hospital stay in mg/kg) by 54% was observed in the treatment arm receiving IV or oral arginine compared to placebo (mean \pm SEM: 1.9 ± 0.4 mg/kg; n=26 vs. 4.1 ± 0.8 mg/kg; n=26, p=0.02; Fig 6A). Pain scores based on a 10-cm visual analog scale of 0-10 reported in the ED or in clinic during initial presentation were similar in both the arginine and placebo group (Fig 1B). As expected, pain scores decreased significantly in both the arginine and placebo arms at time of discharge compared to initial evaluation. However, pain scores were significantly lower at discharge in the arginine arm compared to placebo (Mean \pm SD: 1.9 ± 2.4 vs. 3.9 ± 2.9 , p=0.01, Fig 6B). Comparing the differences in the change from presentation (day 1) to day of discharge adjusting for day 1 values between the placebo and arginine arms, a larger drop in pain scores was also observed in the arginine arm compared to placebo (p=0.01). Average length of hospitalization was 4.5 ± 0.4 days, & there was no significant difference between the 2 groups (4.1 ± 0.3 vs. 4.8 ± 0.5 days, p=0.27; arginine vs. placebo arm), although a clinically relevant trend favored patients treated with arginine. **Total opioid use (mg/kg) correlated strongly to length of hospital stay (r=0.86, p<0.0001), and represents a surrogate biomarker of LOS to evaluate study drug efficacy.** Four episodes of ACS occurred during the study, 3 in the treatment arm and one in the placebo arm. One patient experienced clinical deterioration associated with ACS requiring emergent transfusion & a transfer to the pediatric intensive care unit (PICU) in the placebo arm. No clinical deterioration or PICU transfers occurred in the arginine arm. Five in the treatment arm received transfusion vs. 4 in the placebo arm. No drug-related adverse events were observed. No significant differences were observed between pre & post therapy liver or renal function, or hematological parameters in the arginine treatment group vs. placebo. Arginine is a safe, efficacious and inexpensive intervention with narcotic-sparing effects that should be considered as a potential adjunct to standard therapy for VOE (1, 10, 50).

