The primary goal of this analysis is to compare the standard arginine treatment with placebo. The power analysis is based on this comparison. This sample size calculation is based on a two-sample two-sided t-test, with the objective of detecting a 55% reduction in opioid use from its mean value (4.1) in the placebo group based on the preliminary data generated from the recent [name] arginine trial (1). Based on these findings, the standard deviations are 2.0 and 4.1 (days) in the arginine and the placebo groups, respectively. A sample size of 33 subjects per group has 80% power to detect the treatment effect stated above on a two-sided test at the 0.05 significance level. A secondary goal is to compare the other arginine treatment arm (with a loading dose) to the placebo arm. Finally the two arginine treatments will be compared to determine if there is any difference or trend towards a difference when a loading dose is used that is superior to the standard arginine dose used with success in prior studies. Based on past experiences with arginine therapy, few patients withdrew from the study after the therapy was switched from oral to parenteral. Up to 150 patients will be enrolled, allowing for screen failures and study withdrawal, in order to insure randomization and study completion of 108 patients (36 per group) allowing for a 7% withdrawal rate. We did not adjust the sample size calculations for multiple comparisons as the power calculation only corresponds to the primary goal involving a single comparison of patients receiving the standard treatment or the placebo. We anticipate that the "loading dose" arm will be either the same or better than the standard dose. We will evaluate the efficacy and safety of this loading dose compared to the placebo group.

Each of the comparisons mentioned above will be conducted via a general linear model analysis. Predictors will include the treatment indicator, use of HU, age group, gender and the interactions of each of the last three covariates with the treatment indicator. By including interactions in the model we will be able to determine whether the treatment effect varies across subgroups of patients.

Assistance with statistical analysis and power calculation was provided by the Department of Biostatistics and Bioinformatics at the Rollins School of Public Health, Emory University, by [name] PhD, who will be the biostatistical consultant on this project.

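### The general linear model is left on its constant-variance default although the trial is sized on SDs of 2.0 and 4.1; if all three arms share one fit, the standard errors are wrong in both directions

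*Combined protocol and SAP*

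**What the plan says.** In the Statistical Analysis section the primary goal is standard arginine against placebo. Loading dose against placebo comes second, and the two arginine arms are then compared with each other. On method the plan says "Each of the comparisons mentioned above will be conducted via a general linear model analysis", and on the model's terms: "Predictors will include the treatment indicator, use of HU, age group, gender and the interactions of each of the last three covariates with the treatment". No variance structure, robust error, Welch-type test or transformation is named, and nothing says whether the three comparisons come from one model or three.

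The sample size in the same section rests on unequal spread: "the standard deviations are 2.0 and 4.1 (days) in the arginine and the placebo groups, respectively". The unit is a slip, because the figures match the earlier single-center trial reported in the background: "1.9 ± 0.4 mg/kg; n=26 vs. 4.1 ± 0.8 mg/kg; n=26, p=0.02". No SD is given for the loading-dose arm; the plan says only that it expects this arm to do as well as the standard dose or better. Unequal SDs are explicitly assumed in the length-of-stay power calculation, but that concerns a future phase 3 trial.

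**The concern.** SDs of 2.0 and 4.1 mean a variance ratio of 16.81/4 = 4.2. A general linear model at its default setting estimates one residual variance and uses it for every contrast. If all three arms enter one model, the noisier placebo arm is averaged with two quieter arms. Contrasts with placebo then look more precise than they are, and the contrast between the two arginine arms looks less precise. At stake are the width of the primary confidence interval and the test of the loading dose. The loading dose is a stated objective, but the trial is not sized for it.

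**Working it through.** **Inputs.** SDs 2.0 (standard) and 4.1 (placebo), two-sided alpha 0.05, 80% power, 33 per group, and 36 completers per group after 7% withdrawal, all from Statistical Analysis; 38 randomized per arm, from Study Design and Methods. The background SEMs confirm the SDs: 0.4 × √26 = 2.04 and 0.8 × √26 = 4.08 mg/kg. Assumption: loading-arm SD 2.0, with 1.0 to 4.1 examined.

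**The plan's own figure.** The calculation uses a two-sided t-test for two samples, and its target is given as: "with the objective of detecting a 55% reduction in opioid use from its mean value (4.1) in the placebo group". The difference is 0.55 × 4.1 = 2.255. Then n = (1.960 + 0.842)² × (2.0² + 4.1²) / 2.255² = 32.1, so 33 per group. Power at 33 is 81.0% (normal approximation), 79.9% (equal-variance t) or 79.4% (Welch). The stated 33 is reproduced, and it already uses the two separate SDs.

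**One three-arm fit, 36 per arm.**

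- Pooled SD = √[(4 + 16.81 + 4)/3] = 2.876.
- Model SE for every contrast = 2.876 × √(2/36) = 0.678.
- True SE, either arginine arm vs placebo = √[(4 + 16.81)/36] = 0.760; ratio 0.678/0.760 = 0.89.
- True SE, loading vs standard = √[(4 + 4)/36] = 0.471; ratio 0.678/0.471 = 1.44.

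Simulation with normal data gives 95% interval coverage of about 92% for each arginine arm vs placebo and about 99% for loading vs standard. With arm-specific variances, coverage is 95% for all three.

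**Sensitivity to the loading-arm SD (model SE divided by true SE).**

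| Loading SD | Pooled SD | Standard vs placebo | Loading vs placebo | Loading vs standard |
|---|---|---|---|---|
| 1.0 | 2.70 | 0.84 | 0.90 | 1.71 |
| 1.5 | 2.77 | 0.86 | 0.90 | 1.57 |
| 2.0 | 2.88 | 0.89 | 0.89 | 1.44 |
| 3.0 | 3.15 | 0.98 | 0.88 | 1.24 |
| 4.1 | 3.54 | 1.10 | 0.86 | 1.10 |

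For standard vs placebo the ratio is 1 when (2/3)(20.81 + s²) = 20.81, that is s = 3.23; above that the SE is too large. For loading vs standard it is 1 when (2/3)(20.81 + s²) = 4 + s², that is s = 5.44. That SE is therefore too large over the whole range examined.

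**Separate two-arm fits.** At equal n the pooled variance of the difference is 2 × [(4 + 16.81)/2]/n = (4 + 16.81)/n, which is the true value, so there is no error. With 38 standard and 33 placebo patients, the pooled variance is (37 × 4 + 32 × 16.81)/69 = 9.94. The SE is then √[9.94 × (1/38 + 1/33)] = 0.750 against a true √(4/38 + 16.81/33) = 0.784, ratio 0.957. At 38/36 and 38/34 the ratios are 0.983 and 0.966. With the imbalance reversed they are 1.017 (36/38), 1.035 (34/38) and 1.045 (33/38).

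**Illustrative power, loading vs standard** (36 per arm, both SDs 2.0). At a true difference of 1.0 mg/kg, power is 55% with arm-specific variances and 24% with the three-arm pooled SE. At 0.5 mg/kg it is 18% and 4%.

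**The case against.** The strongest reply is that the plan never specifies a three-arm fit. It speaks of a treatment indicator in the singular, which codes two groups and suits pairwise models at least as well, and pairwise models would match the two-sample t-test behind the sample size. This stands: under that reading the error is nil at equal n. Unequal withdrawal does not rescue the stronger claim, because plausible imbalance moves the SE by only about 2-4%, in either direction. Patients whose drug is stopped for a disqualifying metabolic panel also stay on study under intention-to-treat, which limits loss.

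A reader might infer that the primary test is bound to run above its nominal level. The documents do not support that. With equal means but SDs of 2.0 and 4.1, a three-arm fit does reject in about 8% of simulated trials. In the earlier trial, however, the SD was about equal to the mean in both arms (2.04 against 1.9; 4.08 against 4.1), so if arginine does nothing the SDs may well be equal too, and type I error is then unaffected.

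A reader might also infer that the placebo contrasts and the loading-dose contrast are all distorted by fixed amounts. Only two of the three SDs come from the plan, and the table shows how far the result moves with the third. Finally, the loading-versus-standard comparison is short of power at 0.5 mg/kg under any method, and the plan describes it only as looking for a difference or a trend.

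What remains is that the validity of the intervals rests on a modelling choice that the plan leaves open.

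**Conclusion.** The point holds conditionally, as a cheap improvement rather than a flaw that undermines the trial. The plan's own SDs contradict the constant-variance default, and it neither departs from that default nor says which fit will be used. The 11% and 44% errors require a single three-arm model and a loading-arm SD near 2.0. That SD is an assumption, though it is consistent with the plan's expectation for the arm. The loading-versus-standard error keeps its direction for any loading SD below 5.44; the standard-versus-placebo error does not keep its direction above 3.23. The consequence is for interval width and the loading-dose test when arginine works, not for false positives when it has no effect and the spreads are equal.

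**What to change.** Add to Statistical Analysis a statement of whether one three-arm model or separate pairwise models will be fitted. Prespecify that all arm comparisons use arm-specific residual variances with Satterthwaite degrees of freedom, or alternatively HC3 standard errors. Either is suitable under both readings. Correct the unit on the SDs to mg/kg at the same time.

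The cost is a sentence or two and one software option. The sample size need not change: 33 per group already uses the separate SDs, and a Welch-type analysis has about 83% power for standard versus placebo at 36 per arm. The downsides are small. Relative to a three-arm pooled fit the primary interval would be slightly wider if the loading SD is near 2.0. HC3 is also slightly imperfect at this size: in simulations with covariates and skewed data its coverage for standard versus placebo was 93-94%, against 90-91% for the constant-variance fit.

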Once informed consent is obtained, eligible children and adolescents age 3-21 years will be randomized to one of three study arms: Standard L-arginine dose (100 mg/kg IV TID), one-time L-arginine loading dose (200 mg/kg IV) + standard dose (100 mg/kg IV TID), or placebo (normal saline 1-2 ml/kg IV TID) up to a maximum of 7 days (21 doses) or until discharge, whichever comes first. The maximum loading dose of IV L-arginine will be 20 grams, with a standard dose maximum of 10 gms IV TID. A total of 114 patients will be treated/randomized in this protocol, 38 in each arm. Up to 150 patients may be enrolled, to account for potential screen failures and withdrawals. **Patients must be randomized within 24 hours of receiving their initial parenteral opioid in the ED or clinic/day hospital.** Even though a 24-hr window is established for feasibility, the ideal goal is to randomize and deliver study drug within 2-4 hours in the ED or clinic/day hospital. The average time to study drug delivery in the original [name] Arginine study was 20.4 ± 11 hours (1). Although this original study was not sufficiently powered to detect a decreased length of hospital stay (LOS), the trending decrease by 17 hours is a clinically relevant improvement for patients and their families. A standardized treatment and monitoring protocol for VOE utilized by Emory/Children's Healthcare of Atlanta mutually agreed upon by both the ED and department of hematology will be followed. Pain scores (0-10 scale or FACES as appropriate) will be obtained at presentation to the acute care setting for pain prior to study drug administration and at least TID until discharge. If the patient is discharged from the ED or day hospital/clinic without a hospital admission, a discharge pain score will also be obtained. A discharge blood draw will be obtained whenever possible for those discharged from the ED but will be limited to research labs targeting the arginine metabolome (plasma and erythrocyte amino acids, arginase activity, NO_x and exhaled NO). Information on hydroxyurea use (HU) will be obtained. Randomization will be stratified for HU use to minimize potential confounding effects of HU use. Patients,

physicians, and staff involved in patient care will be blinded as to whether each patient receives arginine vs. placebo.

Patients already participating in the clinical trial may not be enrolled more than once.

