It is provided as a ready-to-use solution and is not typically diluted further. Pediatric doses will be drawn up by the pharmacy. Patients with SCD undergoing growth hormone stimulation test have tolerated 500mg/kg/dose over 30 minutes without complication. In practice, arginine infusion protocols are not typically modified for SCD. No complications with infusions were reported during the arginine trial recently published (1). Arginine compatibility is similar to that of total parenteral nutrition (TPN) and can be co-administered with normal saline/dextrose fluids, ketorolac, opioid analgesia/PCA and antibiotics. There are no issues with IV tubing, which can be changed according to CHOA policy. Although it is a hypertonic solution, the amount of fluid delivered with 1-2ml/kg is minimal and is not anticipated to trigger a pain crisis. In fact our data demonstrated that 1ml/kg of 10% Arginine-HCL given IV TID throughout hospitalization significantly decreased pain scores compared to placebo in children with SCD hospitalized for VOE (1). Past clinical trial experience with arginine did not support the need for a second IV placement specifically for the arginine infusion. Therefore, the clinical IV placed for parenteral opioid therapy will be utilized for study drug. If the IV site should become infiltrated, the IV catheter will be removed and the infiltration addressed clinically as needed, per hospital protocol for IV infiltration. A new IV catheter will be placed if the patient's clinical status mandates continued parenteral opioids or IV access is required for other reasons. If the patient loses his/her IV and it is no longer clinically needed, IV arginine will be discontinued per study protocol. Information on IV infiltration during arginine infusion will be collected and reported as an adverse event.

VOE resolution in patients discharged from the ED or day hospital/clinic and hospital will be defined as the time in hours, of study drug delivery to the time of the last parenteral opioid.

Length of Stay will be defined as the time in hours, of study drug delivery to the time that the discharge order is given in written or electronic form.

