Pain Scores: Pain associated with VOE will be measured on a numeric pain rating scale of 0-10, with the ends representing the extreme limits of "no-pain" (0) and "worst pain" (10), or the FACES pain rating scale when appropriate. Pain scores will be obtained at presentation to the acute care setting for pain prior to study drug administration and at least TID daily, until discharge and at time of discharge.

Specific Aim 2: Safety monitoring

To monitor for potential toxicities associated with a loading dose & repeated administration of IV L-arginine.

Vital signs including blood pressure, hemoglobin, liver and renal function testing will be obtained at the same time as the study blood draw for research labs. Rates of acute chest syndrome, blood transfusion, clinical deterioration, need for intensive care and hospital/ED returns within 72 hours and 30 days will be monitored in all enrolled patients and compared between study arms.

Primary Outcome Measure: *The primary outcome measure is total parenteral opioid use (morphine equivalents mg/kg) calculated from the initial dose of study drug, throughout the ED and/or hospital stay in the arginine arms compared to placebo.*

Secondary Outcome Measures:

Clinical Outcomes

1. Length of hospital stay from study drug delivery to discharge (time of discharge order)
2. Time to VOE resolution after study drug delivery
3. Pain scores at presentation vs. discharge
4. Pain score over time
5. Length of ED stay (time of ED triage to discharge or admission order)
6. ED discharge rate
7. Total opioid dose (mg/kg) in the first 8 hours after study drug delivery
8. Number of study drug doses
9. Rate of acute chest syndrome (not present before randomization)
10. Rate of blood transfusion
11. Change in oxygen saturation and use of supplemental oxygen during admission. PROMIS pediatric Pain and Fatigue short forms (daily for up to 1st 7 days and then on day of discharge: collaboration with [name]/[name])
12. Symptoms questionnaire
13. 72-hour returns and 30-day return visits to the ED or in-patient hospitalizations
14. Diffusion correlation spectroscopy

Study Labs: Clinical, Research and Safety Monitoring

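### Neither pain-score outcome is given a baseline-adjusted analysis, and the presentation pain score, collected before study drug, is not used in the prespecified model

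*Combined protocol and SAP*

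**What the plan says.** The STATISTICAL ANALYSIS section is the only analysis text in the document. It applies a general linear model to each pairwise arm comparison: "Predictors will include the treatment indicator, use of HU, age group, gender", together with the interaction of each of those three covariates with treatment. No baseline measure of the pain episode appears.

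Such a measure is collected. In STUDY DESIGN AND METHODS, Specific Aim 1: "Pain scores (0-10 scale or FACES as appropriate) will be obtained at presentation to the acute care setting". Both that text and the Pain Scores paragraph place this score before study drug.

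The primary outcome is parenteral opioid use "calculated from the initial dose of study drug, throughout the ED and/or hospital stay". Secondary outcomes 3 and 4 are listed only as "Pain scores at presentation vs. discharge" and "Pain score over time". No section says whether the first is a raw discharge score, a change score or a baseline-adjusted score, and none gives a model for the second.

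STUDY OBJECTIVES puts better pain scores in the primary hypothesis beside lower narcotic use. The pilot results in INTRODUCTION AND BACKGROUND report two forms: the raw discharge score, and the fall in pain over the stay adjusted for the first-day score.

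**The concern.** Adjusting for a baseline value of the same measurement is the ordinary way to analyse a follow-up score in a randomised trial. Here the baseline is already scheduled and the pilot used it, but the plan does not carry that analysis forward. Two things follow.

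- **Choice of form.** Raw, change and adjusted analyses of discharge pain can give different standard errors and different p-values. If the form is not fixed, it can be chosen once the results are known, for an outcome named in the primary hypothesis.
- **Precision.** Variation in discharge pain that the presentation score could explain stays in the error term. The same may be true of opioid use, where the planning SD in the placebo arm (4.1) equals the mean (4.1) and the trial has 36 to 38 patients per arm.

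**Working it through.** **1. The plan's own figure.** Inputs from STATISTICAL ANALYSIS: placebo mean 4.1, reduction 55%, SDs 2.0 and 4.1, two-sided 0.05, 80% power. The SDs are labelled as days, but the pilot SEMs of 0.4 and 0.8 with n = 26 give 0.4×√26 = 2.04 and 0.8×√26 = 4.08, so they are in mg/kg.

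- Difference: 0.55 × 4.1 = 2.255.
- Root-mean-square SD: √((2.0² + 4.1²)/2) = 3.226.
- n per arm = 2 × 3.226² × (1.960 + 0.842)² / 2.255² = 32.1, so 33.

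The stated 33 reproduces. A noncentral t with pooled degrees of freedom gives 79.9% at 33; a Welch version needs 34. The calculation is for an unadjusted t-test, so adding a covariate does not invalidate it.

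**2. Discharge pain, 36 per arm.** Pilot SDs at discharge are 2.4 and 2.9 and the pilot difference is 3.9 − 1.9 = 2.0. The documents do not give the correlation r between presentation and discharge scores or the SD at presentation; both are assumed below.

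- Raw: SE = √((2.4² + 2.9²)/36) = 0.627.
- ANCOVA: SE = 0.627 × √((1 − r²)(1 + 1/68)). The factor 1 + 1/68 is the expected cost of chance baseline imbalance with 72 patients and one covariate.
- Change: SE = √(Σ(s² + b² − 2rsb)/36), summed over arms, with s the discharge SD and b the presentation SD.

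| Form | SE, r = 0.3 | SE, r = 0.5 | Power for 2.0, r = 0.3 | Power for 2.0, r = 0.5 |
|---|---|---|---|---|
| Raw discharge score | 0.627 | 0.627 | 88.2% | 88.2% |
| ANCOVA | 0.603 | 0.547 | 90.5% | 95.0% |
| Change, b = s | 0.742 | 0.627 | 75.7% | 88.2% |
| Change, b = 1.5 | 0.621 | 0.546 | 88.8% | 95.1% |

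At r = 0 ANCOVA costs almost nothing: 0.627 × √(1 + 1/68) = 0.632. At r = 0.3 the forms differ by up to 90.5 − 75.7 = 14.8 points of power, or by under 3 points, depending on a presentation SD that the documents do not state. ANCOVA is never materially worse than either alternative in this range.

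**3. Primary opioid model, 36 per arm.** The variance of the treatment difference is (2.0² + 4.1²)/36 × (1 − r²)(1 + 1/68) with one covariate, tested on 69 degrees of freedom. Here r is the correlation of presentation pain with opioid use beyond the terms already in the model. Without the covariate, power is 83.3%.

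| Assumed r | 0 | 0.1 | 0.2 | 0.3 | 0.5 |
|---|---|---|---|---|---|
| Power with covariate | 82.7% | 83.1% | 84.2% | 86.1% | 91.8% |

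Break-even is near r = 0.12; below it the loss is at most 0.6 point.

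**4. Sensitivity to skewness.** Opioid use cannot be negative, and an SD equal to the mean implies skewness. A simulation with gamma outcomes (plan means and SDs) that included the plan's interactions with mean-centred covariates gave changes in power of about −0.7, +0.3, +1.8 and +6 points at latent r = 0, 0.2, 0.3 and 0.5. The normal-error changes are −0.6, +0.9, +2.8 and +8.5. The correlation scales differ, so the comparison is indicative only, but it points to a smaller gain.

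**The case against.** The strongest reply is that leaving a candidate covariate out of a prespecified model is not an error. The plan names its covariates in advance and the comparison is unbiased. No section relates presentation pain to opioid use, and entry requires moderate-to-severe pain, which narrows the score's range. At r up to 0.2 the effect on power lies between −0.6 and +0.9 point. All of this stands for the primary endpoint, so the covariate there is a low-cost option and not a correction.

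The power figures in step 3 also scale a two-arm t-test and do not represent the full model. With the three interactions, the precision of the treatment coefficient depends on coding. Under 0/1 coding of three balanced two-level covariates (assumed), its variance is about four times larger. That is a separate and possibly bigger matter.

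A second reply is that the list of predictors may not be exhaustive. An open list does not prespecify anything, and it still gives no form for the pain outcomes.

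A third is that none of the 14 secondary outcomes has its own analysis form, so pain is singled out. That is fair as a description. Pain is nevertheless in the primary hypothesis, has a pre-treatment counterpart, and was analysed in two forms in the pilot.

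A reader might also infer that the presentation score would correct for patients being at different stages when opioid counting begins. The rule is "Patients must be randomized within 24 hours of receiving their initial parenteral opioid in the ED or clinic/day hospital", against an aim in which "the ideal goal is to randomize and deliver study drug within 2-4 hours". The documents do not support that inference: the score may be up to about a day old when counting starts and may precede opioid treatment, so it does not describe the patient at that moment.

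**Conclusion.** The point holds in a limited form. The firm part is that discharge pain and pain over time lack a stated baseline-adjusted analysis, although the baseline is collected and the pilot adjusted for it. Fixing the form removes a choice that could be made after the data are seen, and ANCOVA is the safe choice: SE 0.603 (r = 0.3) or 0.547 (r = 0.5), against 0.627 for the raw score and 0.546 to 0.742 for a change score. These figures assume the pilot SDs, 36 per arm, the same r in both arms, and presentation SDs that the documents do not give.

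The weaker part is the opioid model. The benefit of adding presentation pain there is unproven and may be negligible, while the cost is at most about 0.6 to 0.7 point of power.

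A reader might infer that the omission biases the treatment comparison or undermines the sample size. It does neither: randomisation protects the comparison, and the 33 per arm reproduces from an unadjusted test.

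**What to change.** **Main change.** State in STATISTICAL ANALYSIS that discharge pain will be compared by ANCOVA with the presentation score as covariate. For a linear model this gives the same treatment estimate as analysing change adjusted for presentation score, so it matches the pilot's adjusted analysis. State that pain over time will use a repeated-measures model with the presentation score as covariate. Name the time points, the within-patient covariance structure, and how scores that end at each patient's own discharge are handled. Say how FACES scores are placed on the 0-10 scale.

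**Secondary change.** Add the presentation pain score to the opioid model as one main effect, without a treatment interaction.

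**Cost.** A short paragraph written before unblinding, with no new data, patients or visits. The repeated-measures details need some thought. If presentation pain turns out unrelated to opioid use, the secondary change costs about 0.6 to 0.7 point of power.
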